### 7.2 Etanercept exposure

In addition to a patient listing of all etanercept exposure, the following tabular summaries will be generated on all enrolled, prospective patients and by completion of initial 24 weeks of etanercept exposure:

- Summary of treatment duration
  - Mean (Standard Deviation (SD)), median and range (in weeks)
  - Proportion receiving  $\leq 24$  weeks of treatment (initial course)
  - Proportion receiving  $> 24$  weeks of continuous treatment (initial course)

## PURPOSE SAP

### Protocol # B1801035

- Summary of patients requiring additional treatment with systemic therapy (etanercept or other non-etanercept therapies)
  - Proportion of patients requiring additional treatment, by subsequent treatment type
- Summary of overall treatment over the entire 5 years of study participation starting from enrollment to the end of follow-up.
  - Duration of exposure to etanercept
  - Cumulative dose of etanercept
  - Total number of treatment periods of etanercept [complete ( $\geq 24$  weeks), incomplete ( $< 24$  weeks) and overall]

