7.4. Primary Analyses

It is anticipated that the etanercept treatment status for each patient will change throughout follow-up. A standard course of etanercept treatment is expected to last 24 weeks. Patients successfully responding to the first etanercept treatment course may be exposed to subsequent treatment (i.e., when patients experience a flare) and the time window between two (or more) consecutive courses of treatment may vary substantially.

Patterns of treatment with etanercept will be described (to the extent possible) as follows:

- Frequency of premature discontinuation of etanercept (i.e., treatment course < 24 weeks)
- Frequency of subsequent treatment with systemic therapies (including re-treatment with etanercept)
- Intervals between etanercept treatment and subsequent course of systemic therapy (including etanercept)
- Means and percentages of demographic and disease characteristics of patients who experience and those who do not experience discontinuation of etanercept
- Frequency of discontinuation stratified by cumulative dose, duration of use, and other etanercept use patterns.

Serious and Pre-specified Opportunistic Infections

Time at risk of serious and pre-specified opportunistic infections will correspond to current/recent treatment with etanercept. Current/recent etanercept treatment will be defined as time between the dates of first and last dose within a treatment course plus 28 days. Risk will be estimated as number of events over cumulative time at risk. Estimates of relative risk of these infections will be used to quantify any association between the study outcomes and current/recent treatment with etanercept. In order to calculate relative risk, incidence of infection during cumulative current/recent treatment with etanercept will be compared to incidence of infection during cumulative period without use of etanercept.

Should any patient develop tuberculosis (TB) during the course of follow-up, the Sponsor will conduct standardised incidence ratio (SIR) analyses using geographically appropriate population based rates of TB applied to time at risk on etanercept.

Analyses may include more than one episode of infection experienced by a single individual. Stratified analyses of the events of interest by etanercept dose, duration of treatment, and

number of treatment course (i.e., first, second, etc.) will be attempted, depending on the number of events reported.

Malignancies

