## **PURPOSE SAP**

**Protocol # B1801035**

Note: Treatment for individual patients may not follow recommendations included in the product labeling, e.g., treatment with etanercept may be reported as continuous and as longer than 24 weeks initially, rather than being reported as discrete treatment periods. Any deviations from the planned analyses will be described in the interim and/or final study reports, as applicable.

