### **9.3 Final study report**

A final registry report will be prepared at closure of the Registry database, when all data collection procedures are completed. The final report will encompass all planned analyses described in this SAP.

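### The SAP omits, without explanation, the protocol's interval from etanercept to the next systemic therapy, and gives its re-treatment proportion no stated denominator and no time frame

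*SAP*

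**What the plan says.** Protocol 7.4 (Primary Analyses) opens its list on treatment patterns with "Patterns of treatment with etanercept will be described (to the extent possible) as follows". One item is the frequency of later systemic therapy, with no denominator given. Another is "Intervals between etanercept treatment and subsequent course of systemic therapy (including etanercept". The fourth objective in both documents rests on these patterns. Protocol 2.1.2 adds that effectiveness is inferred from treatment and re-treatment, not measured directly.

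In SAP 7.2, "the following tabular summaries will be generated on all enrolled, prospective patients and by completion of initial 24 weeks of etanercept exposure". The line on later therapy is "Proportion of patients requiring additional treatment, by subsequent treatment type". The same section also summarises treatment duration, cumulative dose and the number of complete and incomplete periods, and lists all etanercept exposure. SAP 7.7 summarises discontinuation and severity, and lists children who discontinued the initial course with reason, duration and earlier systemic therapies.

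The Note in SAP 5.2.5 foresees that "treatment with etanercept may be reported as continuous and as longer than 24 weeks initially, rather than being reported as discrete treatment periods". SAP 9.3 says "The final report will encompass all planned analyses described in this SAP".

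**The concern.** Two things are missing from the SAP's account of what happens after etanercept.

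- **The interval.** It is the only item in the Protocol 7.4 list that says how long children go between etanercept and the next systemic course. A proportion cannot replace it. A child who restarts after two months and one who restarts after three years count the same, and a child who leaves the registry soon after stopping counts as not re-treated.
- **The denominator.** Re-treatment or switching after stopping can only be observed in a child who has stopped. If children still on their first course sit in the denominator, the figure mixes how often children stop with how often those who stop need something more.

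At stake is objective 4. Without the interval and a defined population at risk, a reader of the final report cannot tell whether a given proportion reflects durable response off drug, continuous use, or short follow-up.

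**Working it through.** Neither document states a figure for this point, so there is nothing to reproduce. The check sets the sections side by side and then sizes the effect under stated assumptions.

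**1. Is the interval anywhere in the SAP text?**
- SAP 5.3.1 repeats that the gap between courses may differ widely, but plans no summary of it.
- SAP 6.6 uses gaps longer than 28 days only as a term in the person-time not at risk.
- SAP 7.2 gives a proportion by type of later treatment; its other summaries describe etanercept exposure itself.
- The SAP 7.7 listing shows therapies before etanercept, not the time to the next one.

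No summary or listing reports the interval, and no reason is given.

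**2. Who is in the denominator?** The 7.2 lead-in names all enrolled prospective patients, split by completion of 24 weeks. SAP 5.3.1 defines completion as at least 168 days of treatment, with no requirement to stop afterwards, so children who never stop are completers.

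**3. Size if only therapy after a stop counts.** Inputs: N = 80, the top of the recruitment target in Protocol 3 and SAP 4. (SAP 6.2 still gives 100 to 200, and the prospective subset may be smaller than the total.) The stopping share and re-treatment share are assumptions.

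Proportion among all = (share who stopped) × (proportion re-treated or switched among stoppers).

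- 56 of 80 stop (0.70) and 34 of the 56 are re-treated or switched. All patients: 34/80 = 42.5% (95% CI 32 to 54%). Stoppers: 34/56 = 60.7% (47 to 74%).
- The ratio of the two equals the stopping share: 0.50, 0.70, 0.90 and 1.00 when 50%, 70%, 90% and 100% stop.
- The 24-week split does not remove this. Take 20 non-completers (all stopped, 12 re-treated) and 60 completers (36 stopped, 22 re-treated). The strata read 12/20 = 60% and 22/60 = 37%, although among completers who stopped it is 22/36 = 61%.

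**4. Size if other things count.** With N = 80, 24 children never stopping and 22/56 = 39% among stoppers, suppose add-on systemic therapy in never-stoppers is counted:

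| Share of the 24 with add-on | All-patient figure |
|---|---|
| 0% | 22/80 = 27.5% |
| 20% (5) | 27/80 = 34% |
| 40% (10) | 32/80 = 40% |
| 80% (19) | 41/80 = 51% |

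Protocol 6.2.2 also lists continued etanercept as the first option under the item on requirement for additional psoriasis treatment. If that item feeds the SAP line, the example in step 3 becomes (34 + 24)/80 = 72.5%, above the 60.7% among stoppers.

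**5. Unequal follow-up.** Assume exponential time to next therapy with median m, and follow-up after stopping uniform on 0.25 to 4.5 years. The true proportion by time t is 1 − 2^(−t/m). For m = 1 year, the crude proportion among stoppers is 73% (simulated), against 75% by 2 years and 96% by 4.5 years. For m = 2 years it is 52%, against 50% and 79%. The crude figure belongs to no stated time.

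**6. Why the interval needs censoring.** If intervals were described only in children who restarted, they would be too short. With an assumed median of 1.5 years, 1 − 2^(−2/1.5) = 60% restart within 2 years and 1 − 2^(−3/1.5) = 75% within 3 years. The median among restarters solves 1 − 2^(−t/1.5) = 0.30 or 0.375, giving t = 0.78 and 1.02 years, against the true 1.5.

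**The case against.** A reader might infer that the plan understates the need for further therapy. The documents do not support that:

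- The SAP line states no denominator; it is inferred from the lead-in.
- The document history mentions a column for retrospective patients in the T3 table series, so the shells may not be limited to prospective patients.
- SAP 5.2.5 words the variable as therapy following the initial course, which leans towards counting only after a stop. The continued-etanercept option in Protocol 6.2.2 leans the other way, and steps 3 and 4 show that the sign of the distortion depends on which applies.
- The proportion among all treated patients is a valid description of treatment patterns, only a different quantity. The protocol's own frequency item has no denominator either, so the SAP does not depart from the protocol there.

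On the interval, the defence is that Protocol 7.4 qualifies the whole list, Protocol 11.4 still ties the final report to the protocol's analyses as well as the SAP's, SAP 5.2.5 promises that deviations will be described, and the table shells were not available to check. All of this is fair, and it means the analysis need not be lost. It does not explain why the SAP text is silent, since the documents provide for collecting start and stop dates for later etanercept periods and information on other systemic treatments at each visit.

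Finally, the registry is descriptive, and the protocol does not ask for Kaplan-Meier curves. True, but describing an interval that many children have not finished requires some handling of censoring, and that involves no hypothesis test.

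**Conclusion.** The omission stands: an analysis listed under the protocol's primary analyses has no counterpart in the SAP text and no explanation. The remaining measure of later therapy is a crude proportion with no time frame and no stated denominator. As a measure of re-treatment or switching after stopping, it can be distorted by children still on their first course.

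The direction and size are not known. If only therapy after a stop counts, the all-patient figure is 0.50 to 0.90 of the figure among stoppers when 50 to 90% stop, and equal to it when all stop. If add-on therapy or continued etanercept counts, it can be higher. All percentages and medians above are illustrations: the documents give no stopping share, re-treatment rate or time to next therapy. The conclusion also assumes that the table shells do not already contain the interval. The SAP should be changed; the safety analyses are not affected.

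**What to change.** In SAP 7.2:

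- Restore the Protocol 7.4 interval as time from the last dose of the first etanercept course that ended during the registry to the start of the next systemic therapy, censored at last follow-up. Use Kaplan-Meier for any next therapy, and cumulative incidence separately for etanercept re-treatment and for other systemic therapy. Count a direct switch as time zero.
- Date other therapies from the recorded start. If none was recorded, use the visit interval (3 months in years 1 to 2, 6 months after that). Protocol 2.2 and SAP 5.3.2 list duration but not start date for these therapies, so this needs checking against the CRF.
- Show the proportion among patients who ended a course beside the all-patient proportion, and report the number still on the first course separately.
- State that continued etanercept is not a subsequent course, and state how add-on therapy is counted.

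The cost is SAP wording and one extra table, with no new data collection. Precision will be limited: with 25 of 42 stoppers re-treated or switched (N = 60), the 95% CI is 43 to 74%; with 34 of 56 (N = 80), it is 47 to 74%. If the interval is judged not feasible, the SAP should say so and why.

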### **7.3 Risk of infection associated with etanercept exposure**

The following patient listings will be generated:

- All serious and opportunistic infections
  - Serious (infection site, pathogen, onset date, resolution date or ongoing, date of last etanercept dose prior to infection)
  - Opportunistic (infection type, nosocomial, onset date, resolution date or ongoing, date of last etanercept dose prior to infection)
  - Concomitant therapies (all) within 28 days prior to each infection
  - Immunosuppressant/steroid use within 28 days prior to each infection

In addition, the following tabular summaries will be presented:

- Number of unique patients, total number of events, and incidence rate of all reported serious and opportunistic infections (by MedDRA System Organ Class (SOC) and Preferred Term (PT))
- Overall incidence rate, stratified by exposure type (current/recent and past)
- Overall incidence rate, stratified by treatment period ( $\leq 24$  weeks,  $> 24$  weeks) during any period of etanercept treatment
- Summary of use of other immunosuppressants or steroids within 28 days prior to serious and opportunistic infection
- Summary of baseline characteristics (demographic and clinical characteristics) stratified by infection status (none reported, reported in association with current or recent exposure, reported in association with past exposure, and specifically associated with initial course)
- Summary of number of infections reported per patient (overall and by exposure status)
- If an adequate number ( $\geq 5$ ) of infections are recorded in each of the current/recent and past treatment groups, relative risk (95% CI) of infection will be calculated as the

## PURPOSE SAP

### Protocol # B1801035

incidence rate ratio (current/recent vs. past treatment with etanercept). The 95% CI was constructed using the formula below.

$$\hat{IRR} = \frac{a}{PT_1} \bigg/ \frac{b}{PT_2}$$
$$\hat{IRR}_L = \left( \frac{PT_2}{PT_1} \right) \left( \frac{a}{b+1} \right) \frac{1}{F_{\alpha/2, 2(b+1), 2a}}$$
$$\hat{IRR}_U = \left( \frac{PT_2}{PT_1} \right) \left( \frac{a+1}{b} \right) F_{\alpha/2, 2(a+1), 2b}$$

Where a and b are the number of infections during the current/recent and past treatment with etanercept, respectively, and PT1 and PT2 are the cumulative patient-year follow-up for the current/recent and past treatment with etanercept, respectively [2].

- If any reports of tuberculosis are identified, standardized incidence ratio (SIR) (95% CI) will be calculated adjusting for age and sex (local population-based rates of tuberculosis will be used).

#### 7.4 Risk of malignancy associated with any etanercept exposure

All malignancies reported will be presented as a listing, including malignancy type (verbatim and MedDRA PT, date of diagnosis and date of resolution (if applicable)), all reported prior drug exposures (up to the time of diagnosis), interval between first etanercept exposure and diagnosis of malignancy, duration of actual exposure (excluding temporary interruptions, if any), and total cumulative exposure.

Risk of incident malignancy in patients who have ever received etanercept will be estimated as number of events over the total time at risk, defined as the time since first dose. If any patients do develop a malignancy during follow-up, incidence rates will be presented and SIR analyses using geographically appropriate population-based norms (age and gender-adjusted) may be used, depending on the data available:

- Incidence rate and SIR (95% CI), for all cancers reported excluding non-melanoma skin cancer and cancer in-situ (primary analysis)

If any patients develop the following specific type of malignancy during follow-up:

- Incidence rate and SIR (95% CI), limited to hematopoietic cancers (secondary analysis)
- Incidence rate of non-melanoma skin cancer (NMSC), and SIR (95% CI) if appropriate population-based rates for NMSC are available (secondary analysis)

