Time at risk of incident malignancies will be defined as time since the date of first dose of etanercept treatment to the date of malignancy diagnosis or end of follow-up if no malignancy has been diagnosed. Long-term risk of incident malignancy in patients who have ever received etanercept will be estimated as number of events over the total time at risk. Should any patient develop cancer during follow-up, the Sponsor will calculate SIRs for malignancy (age and gender-adjusted) using geographically appropriate population-based norms. Although all malignancies reported throughout the study will be described, only the first diagnosis of malignancy occurring during the follow-up will be considered in the SIR analysis.

Other SAEs

Time at risk of all other SAEs will correspond to current/recent treatment with etanercept. Current/recent etanercept treatment will be defined as time between the dates of first and last dose within a treatment course plus 28 days.

A descriptive analysis of SAEs will be conducted. Any grouping and stratification will be dependent on the number and type of events reported.

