7.6. Limitations of the Registry

The planned registry offers as strengths the long-term follow-up during and after treatment with etanercept in a population of paediatric psoriasis patients in the EU. Such a setting will allow fulfilment of the objectives of this registry. However, the registry also carries some limitations. As in any registry, lack of an internal ‘untreated’ contemporaneous comparator group may pose some challenges for the interpretation of data. In the evaluation of the risk of serious and pre-specified opportunistic infections, an attempt will be made to make comparisons within the registry population based on current/recent treatment and periods without etanercept treatment. However, such an approach is unfeasible when assessing risk of malignancies and appropriate external comparator groups will be needed to aid in the interpretation of the registry data. Generalizability of the results may be limited by the characteristics of the population that voluntarily enrol in the registry. Attempts will be made

to characterize and compare patients who refuse to participate with patients who agree to enrol in the registry.

The registry will include patients who initiated etanercept prior to enrolment into the registry. There is the possibility that these patients, who must be considered actively treated at the time of enrolment, are substantively different than other patients who were prescribed etanercept at the same time, but did not tolerate therapy or experienced one or more relevant SAEs, potentially resulting in a differential depletion of susceptible (i.e., the effect whereby patients who remain on treatment are those who can tolerate them while those who are susceptible select themselves out of the population at risk). This could lead to an underestimation, or dilution, of the estimated risk of developing an adverse event associated with etanercept in the population with retrospective data collection.

Generalizability of the results may be limited by the characteristics of the population that voluntarily enrol in the registry. Attempts will be made to characterize and compare patients who refuse to participate with patients who agree to enrol in the registry.

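### The SIRs for malignancy and TB are triggered only by an observed case, so the likeliest outcome, zero cases, would yield no expected count and no upper limit on the SIR

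*SAP*

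**What the plan says.** **Malignancy.** Protocol 7.4 estimates risk as events over total time at risk, then adds: "Should any patient develop cancer during follow-up, the Sponsor will calculate SIRs for malignancy". SAP 7.4 begins the same way, without any condition: "Risk of incident malignancy in patients who have ever received etanercept will be estimated as number of events over the total time at risk". Its next sentence is conditional: "If any patients do develop a malignancy during follow-up, incidence rates will be presented and SIR analyses using geographically appropriate population-based norms" may be used, depending on the data available. The bullet marked as the primary analysis (rate and SIR for all cancers except non-melanoma skin cancer and in-situ cancer) sits under that condition.

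**TB.** Protocol 7.4 opens its SIR sentence with "Should any patient develop tuberculosis (TB) during the course of follow-up" and applies population rates to time on etanercept. SAP 7.3 reads: "If any reports of tuberculosis are identified, standardized incidence ratio (SIR) (95% CI) will be calculated".

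**Why an external comparison is planned.** Protocol 7.6 calls the within-registry comparison unfeasible for malignancy and says that "appropriate external comparator groups will be needed to aid in the interpretation of the registry data". SAP 6.4 adds that, with a small sample and rare events, the SIR approach may have limited value.

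Neither document says what the external comparison should show when no case occurs.

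**The concern.** An expected count needs only person-time and population rates. Both exist whether or not anyone develops cancer or TB, so nothing in the method requires waiting for a case.

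The trigger has two consequences. With zero cases, the only comparison bearing on the malignancy objective is absent. A reader of the final report would see neither how few cases were expected nor how large an excess the data could not exclude, and could take silence as reassurance. With one or more cases, the SIR enters the report because a case occurred. Across repeated registries run under this rule, the published SIRs would average well above the true value.

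This registry is a condition of marketing authorisation and describing long-term malignancy risk is one of its four objectives, so the zero-case output should be fixed in advance.

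**Working it through.** The documents give no expected count, background rate or power, so there is no figure of theirs to reproduce.

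**Inputs**
- Patients: 60 to 80 (Protocol 3; SAP 4). SAP 6.2 instead gives 100 to 200.
- Follow-up: at most 5 years each (Protocol 5), so 60 × 5 = 300 to 80 × 5 = 400 patient-years (PY), or 200 × 5 = 1,000 PY at the top of the SAP 6.2 range. Loss to follow-up and the 2018 end date lower this. For malignancy, time before enrolment raises it, because SAP 6.6 counts from first dose.
- Background malignancy rate: **assumed** 10 to 30 per 100,000 PY.

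**Is zero the likeliest count?** For a Poisson count, zero is the most probable value when the mean is below 1. That needs a true rate below 1/300 = 333, or 1/400 = 250, per 100,000 PY. This step uses no outside rate.

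**Formulas.** E = PY × rate. With a true SIR of 1:
- P(0) = exp(−E)
- smallest reportable SIR = 1/E
- mean SIR given that one is reported = 1/(1 − exp(−E))
- exact upper 95% limit for the SIR at zero cases = 3.689/E, where 3.689 = −ln(0.025)
- exact 95% limits for one case = 0.0253/E to 5.572/E

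| PY | Rate per 100,000 | E | P(0) | 1/E | Mean if reported | SIR upper limit at 0 | 95% CI, one case |
|---|---|---|---|---|---|---|---|
| 300 | 10 | 0.03 | 97.0% | 33.3 | 33.8 | 123 | 0.84 to 185.7 |
| 300 | 30 | 0.09 | 91.4% | 11.1 | 11.6 | 41.0 | 0.28 to 61.9 |
| 400 | 10 | 0.04 | 96.1% | 25.0 | 25.5 | 92.2 | 0.63 to 139.3 |
| 400 | 30 | 0.12 | 88.7% | 8.3 | 8.8 | 30.7 | 0.21 to 46.4 |
| 1,000 | 10 | 0.10 | 90.5% | 10.0 | 10.5 | 36.9 | 0.25 to 55.7 |
| 1,000 | 30 | 0.30 | 74.1% | 3.3 | 3.9 | 12.3 | 0.08 to 18.6 |

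With a true SIR of 3, P(0) = exp(−3E) is still 69.8% to 91.4% at 300 to 400 PY.

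**Rate at zero cases:** 3.689/300 = 1.23 and 3.689/400 = 0.92 per 100 PY as exact upper limits.

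**TB** (**assumed** 2 to 50 per 100,000 and 100 to 400 PY on etanercept): E = 0.002 to 0.20 and P(0) = 82% to 99.8%. A single case puts the lower limit above 1 whenever E is below 0.0253. For example, 300 PY at 5 per 100,000 gives E = 0.015 and a lower limit of 0.0253/0.015 = 1.69.

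If the SIR is always reported, its mean over all outcomes equals the true SIR, so the selection disappears.

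**The case against.** A reader might infer that with zero cases the registry would report no malignancy estimate at all. The documents do not support that. Protocol 7.4 and the first of the two SAP 7.4 sentences estimate risk without condition, SAP 6.6 defines the incidence rate without a trigger, and SAP 7 bases interpretation on point estimates with 95% confidence intervals. TB is also a pre-specified opportunistic infection, so it falls under the infection rates that SAP 7.3 tabulates unconditionally. What remains is a conflict inside SAP 7.4, where the following sentence presents malignancy rates only if a case occurs.

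A reader might also infer that the trigger makes a reported SIR wrong. It does not. For any given case the ratio is the same with or without the trigger, and the 1/E floor for one case comes from the small expected count. SAP 7.4 asks for a 95% CI, and for one malignancy that interval includes 1 at every E in the table. The distortion lies in which results get reported.

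Finally, the gain in precision is small: an SIR upper limit of 31 to 123 at zero cases excludes little. SAP 6.2 calls the study descriptive, and SAP 6.4 already warns of limited value. All of this is fair, but the warning does not say what is reported at zero cases, and a wide limit tells the reader more than a blank.

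**Conclusion.** The point holds for the SIRs. Both documents trigger the malignancy and TB SIRs by an observed case, and zero is the likeliest malignancy count at 60 to 80 patients. Its probability is about 89% to 97% under the assumed 10 to 30 per 100,000 PY and a true SIR of 1, or 74% to 90% at 1,000 PY. In that outcome the plan supplies no expected count and no SIR upper limit. Otherwise it supplies an SIR of at least 1/E, about 8 to 33 at 300 to 400 PY, with a very wide interval.

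The sizes depend on background rates that the documents do not give and on near-complete follow-up. That zero is the likeliest count depends only on the true rate being below about 250 to 333 per 100,000 PY. The crude malignancy rate is inconsistently specified, not absent. A further mismatch is that Protocol 7.4 commits to calculating malignancy SIRs while SAP 7.4 only permits them, so even a case does not guarantee one. This is worth correcting before the final report, but it does not invalidate the planned calculations.

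**What to change.** - In Protocol 7.4 and SAP 7.3 and 7.4, remove the case trigger for the primary malignancy analysis and for TB.
- Always report observed cases, person-years, expected cases from country-, age- and sex-specific rates, the incidence rate with exact Poisson 95% CI, and the SIR with exact 95% CI, including at zero cases. For TB, use the on-etanercept person-time that Protocol 7.4 already names.
- Reconcile the unconditional and conditional rate sentences in SAP 7.4, and the protocol's commitment to calculate malignancy SIRs with the SAP's permission to do so.
- Keep the SAP 6.4 caveat beside the results.

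**Cost:** wording changes and one table of expected counts. Reference rates must be obtained even if no case occurs, and the wide limits must be shown and explained.
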